### 7.1.3 *Exploratory endpoints*

To describe the use of preventative and accompanying measures to cope with treatment related adverse events by evaluating:

- physical activity overall and throughout therapy by questionnaire and actigraph.
- occupational status and smoking status
- influence of inflammation measured by inflammatory blood markers on activity level
- quality of life by questionnaire: total score and the four subscores (disease related symptoms – physical and emotional score, treatment side effects, and well-being)
- concomitant medications to cope with related adverse events

## 7.2 *Safety Evaluations*

In this prospective non-interventional study, investigators will collect and report all serious and non-serious adverse events, deaths, and all instances of ‘special situations’ as described in Section 10, starting at the time from signature of ICF up to Follow-up 1. The description of this safety evaluation is a secondary endpoint of this study. The adverse events will be described overall and also according to level of physical activity assessed by questionnaire and actigraph.

## 8 STUDY TREATMENTS

The decision to prescribe cabozantinib /cabozantinib-nivolumab combination will be made prior to and independently from the decision to enrol the subject in this non-interventional study and the treatment should follow the current local SmPC.

## 9 STATISTICAL CONSIDERATIONS

### 9.1 Subject Classification and Definitions

- **Enrolled subject:** Subject who has signed informed consent to participate.
- **Treated subject:** Enrolled subject who received study treatment at least once during the study.

### 9.2 Analysis Population Definitions

At least, the following populations will be used during the statistical analyses:

- **Enrolled population:** All subjects for whom the informed consent has been signed.
- **Full Analysis Set (FAS) / Safety population:** All enrolled subjects who have received at least one dose of study treatment (cabozantinib for mono or cabozantinib and nivolumab for combination treatment).

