Statistical Methods:	
A formal sample size calculation was not done. We intended to include 100 1st line subjects in the analyses, assuming a drop-out rate due to lost to follow-up of 5% 105 subjects had to be enrolled. In the open-label METEOR (cabozantinib), any dose reduction due to an AE occurred in 59.8% of subjects and the study drug was interrupted in 70% of subjects. The rate of treatment discontinuation due to an AE was 9.7% for subjects treated with cabozantinib. With a sample of 100 subjects, the precision of 2-sided 95% confidence interval would have been respectively 5.9%, 9.6% and 9.0% for proportions of 10% of discontinuation, 60% of dose reduction and 70% of interruption.
 
Up to 28 February 2021, 31 subjects were enrolled in the cabozantinib monotherapy group. The landscape of treatment options for advanced and metastatic RCC having changed, cabozantinib monotherapy is only restrictively recommended in guidelines for first line treatment in mRCC patients. Consequently, the treatment group with cabozantinib monotherapy will not be closed but only a limited number of subjects are further expected in this group.
 
In the second treatment group with cabozantinib-nivolumab combination, the intent is to include 167 subjects. Assuming a drop-out rate due to lost to follow-up of 5%, 175 subjects have to be enrolled. In the interventional Checkmate 9ER study, dose reduction occurred in 56.3% of the subjects. The rate of treatment discontinuation of cabozantinib or nivolumab due to an AE was 15.3%.
 
With a sample of 167 subjects, the precision of 2- sided 95% confidence interval (based on simple asymptotic method) will be respectively 5.4% and 7.5% for proportions of 15% of discontinuation and 55% of dose reduction.
 
Data Analysis
 
At least the following populations will be used during the statistical analyses:
 
 
• Included population: all subjects who signed the informed consent form (ICF);
 
• Full Analysis Set (FAS) / Safety population: all included subjects who have taken at least one dose of study treatment.
 

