#### 9.2.1 Populations Analysed

All analyses will be performed on the FAS / Safety population.

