#### **9.4 Statistical/Analytical Methods**

Statistical analyses will be performed by an external Contract Research Organisation (CRO), managed by the sponsor's Medical Affairs Biometrics Department.

A Statistical Analysis Plan (SAP) describing the planned statistical analyses in detail with Tables, Figures and Listings (TFLs) templates will be developed as a separate document. This SAP will detail the rules and conventions used to compute the derived analysis variables and to handle missing data.

Statistical evaluation will be performed using Statistical Analysis System® (SAS®) (version 9.3 or higher).

Due to the non-interventional character of this study the analysis will be mainly based on descriptive methods. Descriptive statistics will be presented as follows:

- Continuous variables: number of observations, number of missing values, mean, 95% CI of the mean, standard deviation (SD), median, quartiles, minimum and maximum.
- Dichotomous or categorical variables: number of observations, number of missing values, frequency and percentage of each of the categories.

Statistical testing will only be carried out for exploratory purposes. Unless otherwise stated, testing will be performed 2-sided with a type 1 error rate set at 5%.

All study data will be presented in listings.

All the analyses will be presented separately for each group, cabozantinib monotherapy and cabozantinib in combination with nivolumab.

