##### **9.4.1 Demographic and Other Baseline Characteristics**

Descriptive summary statistics (n, mean, 95 % CI of the mean, SD, median, quartiles, minimum, maximum) or frequency counts of demographic and baseline data will be presented for the enrolled population.

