##### **9.4.3 Subject Disposition and Withdrawals**

The number of subjects included, and number and percentage of subjects included but not part of the FAS / Safety population will be provided in total.

The numbers and percentages of subjects included in each of the FAS and in each class of the risk for the FAS population will be tabulated by country, study site and in total. The reasons for subject exclusions will also be tabulated by subgroups and in total. In addition, the numbers of subjects who discontinued and completed the study treatment will be tabulated for the FAS by subgroups and in total. Primary reasons for discontinuation of study treatment will also be tabulated for FAS by subgroup and in total.

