#### **9.4.6 Safety Evaluation**

Analyses and summary tables will be presented on the Safety population (by cabozantinib monotherapy and cabozantinib-nivolumab combination therapy).

All AEs will be coded according to the Medical Dictionary for Regulatory Activities (MedDRA) and will be classified by MedDRA preferred term (PT) and system organ class (SOC). Adverse event listings will be presented by subject, SOC and PT.

The incidence of all reported AEs, treatment emergent AEs (TEAEs), SAEs will be tabulated separately. In addition, summary tables for TEAEs will be presented by maximum grading and drug relationship. Treatment emergent AEs associated with dose modification (temporary interruption, reduction or discontinuation) of cabozantinib and TEAEs leading to cabozantinib temporary dose interruption, reduction or discontinuation will also be summarised separately. Similarly, TEAEs associated with delayed dose injection, temporary interruption or discontinuation of nivolumab will be presented. Adverse events will also be described by level of physical activity.

A TEAE is defined as any AE that occurs during the administration of cabozantinib /cabozantinib-nivolumab combination if:

- It was not present prior to receiving the first dose of cabozantinib /cabozantinib-nivolumab combination; or

- It was present prior to receiving the first dose of cabozantinib /cabozantinib-nivolumab combination but the intensity increased during treatment with cabozantinib /cabozantinib-nivolumab combination.

Summary statistics will be presented for ECOG performance status and weight at each visit. Changes from baseline to each postbaseline assessment will be summarised similarly.

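### Read literally, Section 9.2 admits combination subjects to the FAS/Safety population only after a dose of both drugs, unlike the Synopsis and Section 9.1

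*Protocol*

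**What the plan says.** Section 9.2 gives a single set that serves as both Full Analysis Set and Safety population: "All enrolled subjects who have received at least one dose of study treatment (cabozantinib for mono or cabozantinib and nivolumab for combination treatment". Two other places define the same idea without the parenthesis. The Synopsis (Statistical Methods) has "all included subjects who have taken at least one dose of study treatment", and Section 9.1 defines a treated subject as "Enrolled subject who received study treatment at least once during the study".

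The set carries almost all of the analysis. Section 9.2.1 states "All analyses will be performed on the FAS / Safety population", and Section 9.4.6 states "Analyses and summary tables will be presented on the Safety population".

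Three places reach beyond it. Section 9.4.1 says that "frequency counts of demographic and baseline data will be presented for the enrolled population". Section 9.4.3 says that the "number and percentage of subjects included but not part of the FAS / Safety population will be provided in total". Section 9.4 says "All study data will be presented in listings".

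Section 9.2.2 leaves the rules for allocating subjects to populations to a data review meeting before database lock, with a separate meeting before the interim analysis.

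**The concern.** A safety population should hold everyone exposed to a study drug. With the two drugs joined by a plain conjunction in Section 9.2, a subject enrolled for the combination who took cabozantinib but never received nivolumab, or the reverse, does not meet the entry condition. Such subjects can arise: under Section 5.1 enrolment rests on an intention to treat that is settled before study entry, and Section 7.2 collects adverse events from the signing of consent. Their events would be recorded and then omitted from the summary tables.

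That would conflict with the secondary objective in Section 3.2 of describing all serious and non-serious adverse events for each drug cohort. It would also alter the denominator, and possibly the numerator, of the primary proportions for dose reduction, interruption, delayed injection and termination. Because the protocol words its main population in two ways, a programmer could implement either and cite the protocol for it.

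**Working it through.** **Definitions side by side**

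- Section 9.2: one dose of study treatment, with study treatment spelled out for the combination cohort as the two drugs joined by a plain *and*.
- Synopsis and Section 9.1: one dose of study treatment, with no two-drug wording.
- Sections 7.1.1 and 9.4.4.1 write *and/or* where either drug is meant (interruption and, in 9.4.4.1, discontinuation). Section 9.2 does not.
- Section 4.1 treats the combination as ongoing while either drug continues. That sits poorly with an entry rule needing both.
- No section names the cohort in which a combination-intended subject with only one drug is analysed.

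**The plan's own figures (Section 9.3, combination cohort, n = 167)**

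- Half-width of the 95% interval, 1.96 × √(p(1 − p)/n): p = 0.15 gives 5.42 points (stated 5.4); p = 0.55 gives 7.545 points (stated 7.5).
- Probability of seeing at least one case of a 1% adverse event: 1 − 0.99^167 = 81.3% (stated at least 81%).

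These reproduce and do not depend on the point at issue.

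**Illustration of size**

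Inputs from Section 9.3: n = 167 and a 15% discontinuation rate, so 0.15 × 167 = 25.05 expected AE discontinuations. Assumed, because the protocol gives neither: all 167 had at least one dose of either drug; a share of 1% to 10% (k subjects) had only one drug; and a fraction f of those k stopped for an AE.

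Reported rate after exclusion = (25.05 − f × k) / (167 − k).

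| Excluded k (share) | n left | f = 0 | f = 0.5 | f = 1 |
|---|---|---|---|---|
| 2 (1%) | 165 | 15.2% | 14.6% | 14.0% |
| 3 (2%) | 164 | 15.3% | 14.4% | 13.4% |
| 5 (3%) | 162 | 15.5% | 13.9% | 12.4% |
| 8 (5%) | 159 | 15.8% | 13.2% | 10.7% |
| 17 (10%) | 150 | 16.7% | 11.0% | 5.4% |

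Worked line for k = 8: f = 0.5 gives (25.05 − 4)/159 = 13.2%; f = 1 gives (25.05 − 8)/159 = 10.7%; f = 0 gives 25.05/159 = 15.8%.

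The shift from 15% runs from −0.4 to −4.0 points at f = 0.5, from −1.0 to −9.6 at f = 1, and from +0.2 to +1.7 at f = 0. The rate is unchanged when f equals 0.15, the overall rate, so the sign depends on whether AE stoppers are over-represented among those excluded.

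The chance of seeing a 1% adverse event, 1 − 0.99^n, moves from 81.3% to 81.0% (n = 165), 79.8% (n = 159) or 77.9% (n = 150).

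**The case against.** The parenthesis may only name the regimen in each cohort, leaving a single dose as the operative condition. The Amendment 1 form supports this in part: the parenthesis came in when the term study treatment replaced cabozantinib tablets, so it could be a gloss on the new term. The Synopsis and Section 9.1 point the same way. This stands as a possible reading, so the protocol cannot be said to require both drugs beyond doubt. It does not remove the defect, because the literal reading is equally available and would omit exposed subjects.

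A second argument is that allocation rules belong to the data review meetings and the statistical analysis plan. Detail may be settled there. Here, though, the protocol itself states a definition, and in two ways. Leaving the choice to a meeting held when open-label outcomes are already visible is the weaker course, and the interim and final analyses could then follow different readings.

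A reader might also infer more than the protocol supports:

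- That these subjects vanish from every analysis. Section 9.2.1 says so in general terms, but Sections 9.4, 9.4.1 and 9.4.3 keep them in listings, baseline tables and disposition counts, so exclusions would be visible.
- That one-drug-only treatment is often due to early toxicity, or that the bias always favours tolerability. No section gives a rate or a reason. Progression, death or a choice by subject or physician are also possible, and the f = 0 column shows the rate rising.
- That PFS contains immortal time. This would need the literal entry rule, different start dates for the two drugs and a clock started at the first of them. None of these is established. Sections 7.1.2 and 9.4.4.2 start PFS at initiation of the combination without saying what applies if the dates differ.

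Subjects who begin both drugs and later stop one stay in the set under either reading.

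**Conclusion.** The point holds as an inconsistency with a real consequence: one of the protocol's two wordings of its main population, followed literally, leaves subjects exposed to a study drug out of the adverse event tables, the primary proportions and the effectiveness analyses. How many subjects this concerns, and which way it would move the results, cannot be told from the protocol.

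The illustrative shifts rest wholly on the assumed share and on the assumed fraction stopping for an AE. At a 1% share they are at most 1.0 point in either direction, small beside the planned half-width of 5.4 points. Only with a 10% share, all of whom stopped for an AE, does the shift (9.6 points) exceed that half-width. The case for correction rests on the population definition, not on a demonstrated bias.

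**What to change.** In Section 9.2, require at least one dose of cabozantinib and/or nivolumab for the combination cohort, and use the same wording in the Synopsis and Section 9.1. State that a combination-intended subject who received only one drug is analysed in the combination cohort intended at enrolment. Report the number of such subjects alongside the disposition counts in Section 9.4.3. Settle this before the interim data review, so that the interim and final analyses use the same rule.

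The cost is a few sentences of protocol text and a matching line in the statistical analysis plan. No new data are needed, and the sample size statement is unaffected.

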#### 9.2.1 Populations Analysed

All analyses will be performed on the FAS / Safety population.

#### 9.2.2 Subject Allocation and Reasons for Exclusion from the Analyses

The rules for allocation of subjects to each of the analysis populations will be defined and documented during a data review meeting held prior to database lock. An interim data review meeting will be held prior to the planned interim analysis.

### 9.3 Sample Size Determination

A formal sample size calculation is not done. We intended to include 100 1st line subjects in the analyses, assuming a drop-out rate of 5% 105 subjects had to be enrolled. In the open-label METEOR Study, any dose reduction due to an AE occurred in 59.8% of subjects and the study drug was interrupted in 70% of subjects. The rate of treatment discontinuation due to an AE was 9.7% for subjects treated with cabozantinib. With a sample of 100 subjects, the precision of 2-sided 95% confidence interval would have been respectively 5.9 %, 9.6 % and 9.0 % for proportions of 10% of discontinuation, 60% of dose reduction and 70% of interruption. With 100 evaluable subjects the expected 12-months progression-free survival rate of 35% can be estimated with a 95% confidence interval of [0.257; 0.452] and the expected ORR of 20% with one of [0.127; 0.292].

Up to 28 February 2021, 31 subjects were enrolled in the cabozantinib monotherapy group. The landscape of treatment options for advanced and metastatic RCC having changed, cabozantinib monotherapy is no longer recommended as treatment of choice for 1st line treatment in mRCC patients. Consequently, only a limited number of subjects are further expected in this group.

In the second treatment group with cabozantinib-nivolumab combination, the intent is to include 167 subjects. Assuming a drop-out rate due to lost to follow-up of 5%, 175 subjects have to be enrolled. In the interventional Checkmate 9ER study dose reduction occurred in 56.3% of the subjects. The rate of treatment discontinuation of cabozantinib or nivolumab due to an AE was 15.3%. With a sample of 167 subjects, the precision of 2- sided 95% confidence interval (based on simple asymptotic method) will be respectively 5.4% and 7.5% for proportions of 15% of discontinuation and 55% of dose reduction.

Furthermore, with 167 subjects adverse events occurring with a probability of at least 1% will be detected with a probability of at least 81%.

#### **9.4 Statistical/Analytical Methods**

Statistical analyses will be performed by an external Contract Research Organisation (CRO), managed by the sponsor's Medical Affairs Biometrics Department.

A Statistical Analysis Plan (SAP) describing the planned statistical analyses in detail with Tables, Figures and Listings (TFLs) templates will be developed as a separate document. This SAP will detail the rules and conventions used to compute the derived analysis variables and to handle missing data.

Statistical evaluation will be performed using Statistical Analysis System® (SAS®) (version 9.3 or higher).

Due to the non-interventional character of this study the analysis will be mainly based on descriptive methods. Descriptive statistics will be presented as follows:

- Continuous variables: number of observations, number of missing values, mean, 95% CI of the mean, standard deviation (SD), median, quartiles, minimum and maximum.
- Dichotomous or categorical variables: number of observations, number of missing values, frequency and percentage of each of the categories.

Statistical testing will only be carried out for exploratory purposes. Unless otherwise stated, testing will be performed 2-sided with a type 1 error rate set at 5%.

All study data will be presented in listings.

All the analyses will be presented separately for each group, cabozantinib monotherapy and cabozantinib in combination with nivolumab.

##### **9.4.1 Demographic and Other Baseline Characteristics**

Descriptive summary statistics (n, mean, 95 % CI of the mean, SD, median, quartiles, minimum, maximum) or frequency counts of demographic and baseline data will be presented for the enrolled population.

##### **9.4.2 Homogeneity of Groups**

The risk score as part of the primary endpoint will split up the population in the following categories: favourable, intermediate and poor risk. This will be done either by IMDC [8] or MSKCC [9] risk score in the decision of the investigator. Description of demographic and baseline characteristics by risk group will be used to assess homogeneity. No comparison test will be performed.

##### **9.4.3 Subject Disposition and Withdrawals**

The number of subjects included, and number and percentage of subjects included but not part of the FAS / Safety population will be provided in total.

The numbers and percentages of subjects included in each of the FAS and in each class of the risk for the FAS population will be tabulated by country, study site and in total. The reasons for subject exclusions will also be tabulated by subgroups and in total. In addition, the numbers of subjects who discontinued and completed the study treatment will be tabulated for the FAS by subgroups and in total. Primary reasons for discontinuation of study treatment will also be tabulated for FAS by subgroup and in total.

#### **9.4.4 Primary and Secondary Evaluations**

##### *9.4.4.1 Primary Endpoint Analysis*

The proportion of subjects with  $\geq 1$  dose reduction of cabozantinib due to AE will be described with its 95% confidence interval, by risk group and overall.

The same analysis will be presented for the proportion of subjects with  $\geq 1$  dose interruption of cabozantinib and/or nivolumab, delayed dose injection of nivolumab and discontinuation of cabozantinib and/or nivolumab due to AE.

##### *9.4.4.2 Secondary Endpoint Analysis*

The secondary endpoints will be analysed descriptively by risk group and overall.

ORR and DCR will be described at each time point (W8, W16, W24, W32, W40, W46 and W52). The progression free survival, defined as time from cabozantinib /cabozantinib-nivolumab combination initiation to disease progression or death will be analysed using standard survival analysis methods including Kaplan-Meier product-limit survival curve. The median time to event will be estimated and presented with its 95% confidence interval.

The subjects still alive without disease progression at the end of the follow-up will be censored at their last assessment date.

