### 4.1 Overview

This is an international, multicentre, non-interventional prospective study. Data will be collected via electronic case report form (eCRF) by the sites.

This study will be conducted in Germany and Austria, which have a cabozantinib tablets Marketing Authorisation (MA) for first line use. MA for the cabozantinib-nivolumab combination as first line treatment in advanced or metastatic RCC was in March 2021. Patients intended to be treated with this combination can be enrolled as soon as the MA is in place for use of these products in the European Union.

Investigators will follow their individual therapeutic concept for the treatment with cabozantinib or cabozantinib-nivolumab combination in accordance with the current SmPC.

No out-of-routine diagnostic or therapeutic intervention is allowed during this study. All data recorded in this study originate from routine diagnostic and therapeutic procedures.

The investigator needs to inform the subject that personal and medical data will be recorded for this study. The subject has to give written informed consent for data collection, data processing and for monitoring purposes.

Data will be collected at the described visits:

- Visit 1 (baseline): enrolment visit,
- Visit 2 (approximately 4 weeks after baseline),
- Visit 3 (approximately 8 weeks after baseline),
- Visit 4 (approximately 12 weeks after baseline),
- Visit 5 (approximately 16 weeks after baseline),
- Visit 6 (approximately 24 weeks after baseline),
- Visit 7 (approximately 32 weeks after baseline),
- Visit 8 (approximately 40 weeks after baseline),
- Visit 9 (approximately 48 weeks after baseline),
- Visit 10 (approximately 56 weeks after baseline),
- Follow-up 1 (30 days after treatment discontinuation),
- Follow-up 2 (1 year after treatment discontinuation or 24 months after baseline if subjects reached visit 10).

The timing of the visits according to routine clinical practice is assumed to be close to the proposed schedule. If the timing does not meet the schedule, entries should be made at the visit nearest in time to the proposed schedule.

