### Visits 2/3/5/7/9 - (about 4, 8, 16, 32 and 48 weeks, respectively, after baseline)

- Visit date
- Evaluation of tumour (Overall response)
- ECOG Performance Status
- Vital Signs (Body weight, blood pressure)
- Adverse Events
- Concomitant medication for AEs
- Cabozantinib regimen (Start date, stop date, dose, frequency, time of day of intake, primary reason for dose change or discontinuation)
- Nivolumab regimen (dose and date of injection, reason for injection delayed if any and primary reason for nivolumab discontinuation)
- Study discontinuation or completion form (in case of discontinuation: reason for premature withdrawal)

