### Visits 4/6/8/10 - (about 12, 24, 40 and 56 weeks, respectively, after baseline):

- Visit date

- Evaluation of tumour (Overall response)
- ECOG Performance Status
- Adverse Events
- Concomitant medication for AEs
- Cabozantinib regimen (Start date, stop date, dose, frequency, time of day of intake, primary reason for dose change or discontinuation).
- Nivolumab regimen (dose and date of injection, reason for injection delayed if any and primary reason for nivolumab discontinuation)
- Smoking status and Occupational status
- Vital Signs (Body weight, blood pressure)
- Inflammatory blood markers (hsCRP or CRP, as available, no safety marker)
- Quality of life questionnaire (NFKSI-19) after the visit
- Activity questionnaire after the visit
- Actigraph measurement (1 week) after the visit [only in centres where activity measurement is part of clinical routine]
- Study discontinuation or completion form (in case of discontinuation: reason for premature withdrawal)

Follow-up visit (FU) 1 - (about 30 days after treatment discontinuation):

- Visit date
- Adverse Events
- Concomitant medication for AEs
- Post Cabozantinib / cabozantinib-nivolumab combination systemic treatment for RCC
- Study discontinuation or completion form (in case of discontinuation: reason for premature withdrawal)

Follow-up visit (FU) 2 - (1 year after treatment discontinuation or 24 months after visit 1):

- Visit date
- Adverse Events
- Concomitant medication for AEs
- Post Cabozantinib /cabozantinib-nivolumab combination systemic treatment for RCC
- Cabozantinib regimen (dose and date for last cabozantinib intake; only for patients who continued until visit 10)
- Cabozantinib-nivolumab combination regimen (dose and date for last cabozantinib and nivolumab intake; only for patients who continued until visit 10)
- Study discontinuation or completion form (in case of discontinuation: reason for premature withdrawal)

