### 7.1.2 *Secondary Endpoints & Evaluations*

- To describe the effectiveness of cabozantinib /cabozantinib-nivolumab combination in advanced or metastatic RCC in real-life in terms of progression free survival (PFS), and best overall response (ORR & DCR).
  - Progression free survival is defined as the time between the start date of cabozantinib /cabozantinib-nivolumab combination and the date of progression or death from any cause. Disease progression is defined as either radiological progression assessed by the investigator using RECIST 1.1 [7] or clinical progression.
  - The best overall response is the best response assessed by investigator recorded during the treatment period.
  - ORR is defined as the proportion of subjects achieving complete or partial response.
  - DCR is defined as the proportion of subjects achieving a complete response, partial response or stable disease.
- To describe the impact of the activity level at the beginning of the treatment (within the first 2 weeks of cabozantinib /cabozantinib-nivolumab combination intake) on the occurrence of adverse events (AEs) using the actigraph and questionnaires
- To describe the use of cabozantinib /cabozantinib-nivolumab combination in subjects with advanced or metastatic renal cell carcinoma (mRCC) treated in real-life clinical setting in 1st line treatment split by histological subtype (clear cell and non-clear cell) in terms of:
  - Number and proportion of subjects with dose reductions of cabozantinib due to SAEs/AEs
  - Number and proportion of subjects with dose interruption of cabozantinib and/or nivolumab due to SAEs/AEs
  - Number and proportion of subjects with termination of cabozantinib /cabozantinib-nivolumab combination due to SAEs/AEs
  - Number and proportion of subjects with injection delayed of nivolumab due to SAEs/AEs

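### The ORR/DCR time points include W46 and W52, when no visit exists, and omit W48 and W56; the only specific ORR/DCR analysis is by time point, while the endpoint is defined as best response over treatment

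*Protocol*

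**What the plan says.** Section 9.4.4.2 opens by giving all secondary endpoints a descriptive analysis, by risk group and overall. Its one specific sentence on tumour response is: "ORR and DCR will be described at each time point (W8, W16, W24, W32, W40, W46 and W52".

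The visit schedule is in section 4.1, Table 2 and section 6.1. The last two on-treatment visits are "Visit 9 (approximately 48 weeks after baseline" and "Visit 10 (approximately 56 weeks after baseline". Section 6.1 groups the visits as "Visits 2/3/5/7/9 - (about 4, 8, 16, 32 and 48 weeks, respectively, after baseline" and "Visits 4/6/8/10 - (about 12, 24, 40 and 56 weeks, respectively, after baseline". Both groups include the item "Evaluation of tumour (Overall response", and Table 2 ticks overall response at Visits 2 to 10 and at neither follow-up visit. For visits that fall off schedule, section 4.1 says: "If the timing does not meet the schedule, entries should be made at the visit nearest in time to the proposed schedule".

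Section 7.1.2 defines the endpoint: "The best overall response is the best response assessed by investigator recorded during the treatment period". ORR and DCR are then proportions of subjects reaching the relevant response categories. Section 9.3 gives the precision for one expected ORR of 20% with 100 evaluable subjects, a 95% CI of 0.127 to 0.292.

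**The concern.** The protocol does not leave the response time points to the SAP. It states them, and two of them cannot be produced from the visits it schedules. A SAP that follows the list inherits the error; a SAP that corrects it departs from the protocol. Without a correction, the analyst must decide which visits the last two columns of the table stand for.

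The second issue is which ORR and DCR will be reported as the result. The definition gives one best response per subject, hence one proportion per cohort. The specific analysis gives seven proportions by week and does not say which of them, if any, is the endpoint. These are different quantities, so a reader of the report could take a by-visit rate for the ORR defined in 7.1.2.

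**Working it through.** **Step 1. Compare the two lists.** Inputs: analysis weeks from section 9.4.4.2; visit weeks from sections 4.1 and 6.1 and Table 2.

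| Visit | Week of response evaluation | In the 9.4.4.2 list? |
|---|---|---|
| 2 | 4 | no |
| 3 | 8 | yes |
| 4 | 12 | no |
| 5 | 16 | yes |
| 6 | 24 | yes |
| 7 | 32 | yes |
| 8 | 40 | yes |
| none | 46 | listed, but no visit |
| 9 | 48 | no |
| none | 52 | listed, but no visit |
| 10 | 56 | no |

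Five of the seven listed weeks match a visit and two do not. Four of the nine scheduled response evaluations are absent from the list: weeks 4, 12, 48 and 56.

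**Step 2. Does the nearest-visit rule place the two weeks?**

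- W46: |46 − 48| = 2 and |46 − 40| = 6, so the nearest visit is Visit 9.
- W52: |52 − 48| = 4 and |52 − 56| = 4, a tie between Visits 9 and 10.

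The rule therefore suggests a home for W46 and none for W52.

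**Step 3. Is the list a deliberate convention?** The next section, 9.4.4.3, describes activity and quality of life at W12, W24, W40 and W56. These are Visits 4, 6, 8 and 10, all real. So the chapter elsewhere labels time points by scheduled visit, and W46 and W52 are out of line with it. The absence of W4 and W12 has a plausible history: the Amendment #1 form shows that response was formerly not evaluated at Visits 2 and 4. Leaving them out of a by-visit table is in any case a permissible choice.

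**Step 4. Which ORR does section 9.3 plan for?** Exact (Clopper-Pearson) interval for x = 20 of n = 100:

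- lower limit = 2.5% quantile of Beta(20, 81) = 0.1267
- upper limit = 97.5% quantile of Beta(21, 80) = 0.2918

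This reproduces the stated interval of 0.127 to 0.292. The planned precision refers to one proportion, which fits the definition in 7.1.2 and not a series of weekly rates.

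**Step 5. How do by-visit and best-response rates relate?** Take the FAS as denominator for both, as section 9.2.1 directs, and a visit within the treatment period. Every subject in response at that visit is also a best-response responder, so the by-visit ORR cannot exceed the ORR of 7.1.2. It equals that ORR only if every responder is recorded in response at that same visit. A subject with a partial response at W8 and progression at W24 counts in the defined ORR but not in the W24 rate. The same holds for DCR.

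**The case against.** The strongest reply is that this is a labelling slip. The first five entries match Visits 3, 5, 6, 7 and 8; only Visits 9 and 10 remain, so in list order W46 must mean Visit 9 and W52 must mean Visit 10. Data are recorded by visit at approximate weeks, and nothing is lost. This is probably what was intended. It does not make the text right: the reader must override two stated weeks, and the protocol's own nearest-visit rule does not lead to Visit 10 for W52.

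Three stronger readings are tempting, and the documents do not support them.

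- *Best overall response has no analysis, so the planned ORR will not be estimated.* The first sentence of 9.4.4.2 covers all secondary endpoints, and section 9.4 provides frequencies and percentages for categorical variables. What is missing is a specific statement, not an analysis.
- *The unlisted evaluations are never used.* Any response recorded during treatment counts towards best overall response, progression at any visit counts towards PFS, and all study data are to be listed.
- *By-visit rates will describe only the selected subjects still on treatment.* Section 9.2.1 places all analyses on the FAS, and 9.4.4.2 states no on-treatment denominator.

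It can also be said that 9.4.4.2 adds to the definition in 7.1.2 without withdrawing it, and that a rate at a time point could mean best response up to that time. Both are fair, and the text does not say which meaning applies. On the cumulative reading, the last entry would come closest to the endpoint, and that entry is W52, which has no visit.

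**Conclusion.** The point holds in two parts. First, as a matter of plain comparison, two of the seven ORR/DCR time points do not exist in the schedule, and the last two scheduled tumour evaluations are not listed. This needs no assumption and does not depend on the SAP. Second, the only specific ORR/DCR analysis is by time point, which does not match the treatment-period best response in 7.1.2 or the single ORR in 9.3. This is a mismatch in specification; it does not show that the defined ORR will go unreported.

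The size is modest. The endpoints are secondary, the study is descriptive without formal testing, and neither data collection nor the endpoint definition is affected. It is still worth correcting, because the rule is wrong as written and cheap to repair.

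**What to change.** In section 9.4.4.2:

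1. Replace the list of weeks with W8, W16, W24, W32, W40, W48 and W56. W4 and W12 may be added, since overall response is recorded there too.
2. State that ORR and DCR based on best overall response over the treatment period, in the FAS and with 95% CI, are the endpoint analysis, overall and by risk group within each treatment cohort, and that the by-visit figures are supportive.

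The CI method and the handling of subjects without any response assessment can be left to the SAP. The cost is two sentences, with no new data and no change to the visit schedule; the SAP's response tables should be checked against the corrected list.
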